2. OBJECTIVES & OUTCOME MEASURES / ENDPOINTS

OVERALL AIM

The overall aim is to conduct a two-arm multicentre, rater-blind, randomised controlled trial comparing CBT_{BAR} plus TAU vs. TAU only for BAR individuals to evaluate the efficacy of a specific intervention (CBT_{BAR}). We also aim to investigate how CBT_{BAR} impacts on the pathway between key psychological processes and mood swings. The overarching research questions are:

- 1) To what extent is CBT_{BAR} (a psychological therapy) effective in reducing distressing mood swings when compared to Treatment As Usual (TAU) for BAR individuals? (*Measured at 27-weeks follow-up*)
- 2) Investigate how CBT_{BAR} impacts on the pathway between key psychological processes and mood swings measured at 17-week follow-up.
- 3) What are the perceptions of patients and health care professionals regarding the implementation of this therapy in NHS services?

EFFICACY AIMS

The trial has a number of efficacy aims:

- 1) To determine the efficacy of CBT_{BAR} (a specifically developed psychological therapy) in reducing distressing high and low mood swings when delivered to patients meeting BAR criteria.
- 2) To determine whether positive effects of CBT_{BAR} last over a 52-week follow-up period.
- 3) To investigate patients', health care professionals, and NHS stakeholders' perceptions of implementation of CBT_{BAR}.

Primary Objective

To determine the efficacy of CBT_{BAR} (a specifically developed psychological therapy) in reducing distressing high and low mood swings when delivered to participants meeting BAR criteria.

Primary Outcome Measure/Endpoint

Mood swing symptom severity assessed by SCID-5 + PSR's (SCID LIFE) [1] at 27-week (post treatment) as measured by the PSR scores as an average of the prior 4 weeks. A longitudinal severity rating of overall symptom levels for each week over the time period (prior 4 weeks) is completed providing two LIFE scores, one for mania and one for depression [1].

Mechanism Objective

To investigate the extent to which CBT_{BAR} impacts on distressing high and low mood swings (SCID-5 + PSR's (SCID LIFE)) via extreme positive and negative appraisals of internal states (HAPPI) which then impacts on subsequent behaviours (BC) used to control mood (ISS).

Mechanism Measures/Endpoint

- 17-week (during therapy): Hypomanic Positive Predictions Inventory (HAPPI), the Behaviour Checklist (BC) and Internal States Scale (ISS)
- Participants' perceptions of how CBT_{BAR} effects psychologically driven appraisals and subsequent behaviours that control mood in the pathway to high and low mood states derived from qualitative interviews (after therapy cessation).

Secondary Objectives

To determine the efficacy of CBT_{BAR} in:

- reducing distressing high and low mood swings at 52-week follow-up period
- the likelihood of transition to BD in comparison to TAU alone over a 52-week follow-up time period
- the reduction of key problematic psychological processes over a 52-week follow-up period
- improved functioning and quality of life compared to TAU alone over a 52-week follow-up time period

Secondary Outcome Measurement/Endpoint

Mood Swings measured at 17-, 27-, and 52- week follow-up points:

- Psychiatric Rating Status scores (SCID LIFE) [1]):
 - Mood swing symptom at 52-week as measured as an average of the prior 4 weeks;
 - % of time in subthreshold symptoms;
 - residual or recovered time periods;
 - time in symptoms (% of overall time and no of weeks during follow-up intervals) [60, 61];
 - number of 'well' weeks as defined as weeks with none or minimal symptoms
- Structured Clinical Interview for Axis 1 Diagnoses (SCID- 5; [62]): Semi structured interview assessing mood diagnoses at 17-, 27- and 52-week follow up.
 - o capturing time to transition to first episode (hypo)mania)
 - time to recovery from subthreshold (BAR) symptoms will also be captured over the 52-week follow-up period

Appraisals of and responses to mood (hypothesised mechanisms) measured at 17-, 27-, and 52- week follow-up points:

- Hypomanic Positive Predictions Inventory (HAPPI; [63]): a self-report measure assessing for multiple, extreme, and personalised appraisals about high and low mood at 27- and 52-week follow-up.
- Behaviour checklist (BC;[64]): a 21 item questionnaire of ascent, normalising and descent behaviours and internal states
- Internal State Scale (ISS; [65]): measuring the severity of mood states (self-report) at 27- and 52-week follow-up

Self-report mood swing questionnaires, measured at 27-, and 52- week follow-up points:

- Beck Depression Inventory (BDI-II; [66]): measuring the severity of depression (self-report) at 27- and 52-week follow-up.
- Young Mania Rating Scale (YMRS; [67]): semi-structured interview assessment of high mood at 27- and 52-week follow-up.
- Altman Self Rating Scale (ASRS; [68]): measuring high mood experiences (self-report) at 27- and 52-week follow-up.

Health Utility, measured at 27-, and 52-week follow-up points:

- Service Use Interview (adapted for this study): use of formal and informal health and social care at 27and 52-week follow-up.
- Health Questionnaire (EQ-5D-5L; [69]): health status and health related utility scores of participants at 27- and 52-week follow-up.
- Recovering Quality of Life (ReQoL; [70]):

Functioning, measured at 27-, and 52- week follow-up points:

- Global Assessment of Functioning scale (GAF; [71]): measure of an individual's level of social, occupation and psychological functioning at 27- and 52-week follow-up.
- Social and Occupational Functioning Assessment Scale (SOFAS; [72]):_Additional measure of an individual's level of social & occupational functioning at 27- and 52-week follow-up.
- World Health Organisation Quality of Life (WHOQOL-BREF; [73]): will be administered to assess quality of life.

Additional secondary outcomes, measured at 27-, and 52- week follow-up points:

- Pittsburgh Sleep Quality Inventory (PSQI; [74]): Measure quality of sleep at the 27- and 52-week followup.
- Positive and Negative Sleep Appraisal Measure (PANSAM;[75]): Measure appraisals of sleep across high and low mood states at the 27- and 52-week follow-up.
- Metacognition Questionnaire (MCQ-30;[76]): at 27- and 52-week follow-up
- Desire Thinking Questionnaire (DTQ; [77]): at 27- and 52-week follow-up
- Response Style Questionnaire (RSQ; [78]): at 27- and 52-week follow-up
- Brief Core Schema Scale (BCSS; [79]): at 27- and 52-week follow-up
- All additional treatments in both arms will be monitored using a service use interview and LIFE ratings of pharmacological and psychosocial treatments for all mental health contacts, frequency of sessions, length of treatment, and number of days of inpatient and partial hospitalisation. Medication usage and dosing are recorded on a weekly basis as important confounders.

Qualitative Objectives

To understand how participants experience or perceive the intervention to have impacted on their mood, behaviours and symptoms and draw patterns across participants' experiences.

To identify key themes associated with the implementation of CBT_{BAR} from the perspective of key stakeholders

Qualitative Measure/Endpoint

A qualitative topic guide (after the end of therapy, post 27-weeks will be employed to identify how participants experience or perceive the intervention to have impacted on their mood, behaviours and symptoms and draw patterns across participants' experiences. We will seek to identify components of the intervention that participants continued to utilise beyond therapy, and ways they have incorporated these into their lives.

A qualitative topic guide (after the end of therapy, post 27-weeks) for key stakeholders will be utilised to identify potential barriers and solutions to future implementation.

Hypotheses

Our outcome measures are designed to test the following hypotheses.

Efficacy Hypotheses

- 1) CBT_{BAR} + TAU will lead to improvement in mood swings (SCID-5 + PSR's (SCID LIFE)) compared to TAU alone at
 - a. end of treatment (27-week follow-up)
 - b. follow-up (52-week follow-up).
- 2) CBT_{BAR} + TAU will reduce the likelihood of transition to BD in comparison to TAU alone over a 52-week follow-up time period.

3) CBT_{BAR} + TAU will lead to improved functioning and quality of life compared to TAU alone over a 52week follow-up time period.

Mechanistic Hypotheses

- 1) CBT_{BAR} + TAU will reduce extreme positive and negative appraisals of internal states (HAPPI) and subsequent behaviours used to control mood (BC) at 27 weeks.
- 2) The mechanism by which CBT_{BAR} causes improvement in mood swings (SCID-5 + PSR's (SCID LIFE)) is due to the reduction of extreme positive and negative appraisals of internal states (HAPPI) which in turn improves subsequent behaviours used to control mood (BC) and then internal states (ISS).

Internal Pilot Progression Criteria

An internal pilot will be conducted with a proposed length to month 16 (month 7 of recruitment). By month 16 (γ_3 of the entire recruitment window, month 7 of the recruitment timeline) we plan to recruit γ_3 (68) of our total target (338), see table 1. This will be monitored by the trial management group and reviewed by the Trial Steering Committee as necessary

% / Threshold*	Red	Amber	Green
Trial recruitment	<60% of target (68)	60-99% of target (41-67)	≥100%
	≤40 recruited	41-67	≥68
Recruitment rate/ site/ month	≤1.6	1.6-2.1	≥2.2
Number of sites opened	1-2	3-4	5
Proportion receiving allocated intervention	<90% (≤61)	90-94% (62-64)	≥95% (65)

Table 1. Internal pilot progression criteria at month 16 (month 7 of recruitment window) based upon recruiting 1/5 of total target (threshold = 68*)

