than for mania. On the LIFE PSR, our eligible population will score at the higher end of the subthreshold range (3-4) as those scoring 5-6 will confer research diagnostic criteria and therefore not meet the inclusion criteria for the trial; based on our pilot trial (mean baseline BDI-II score of 37.9), participants will tend to be towards the upper end of the subthreshold range (i.e. mean around 3.75). Button [81] reported that a MCID for the BDI-II is around 17-18%; given that we expected similar sensitivity for the mean LIFE depression PSR scores as would be the case for BDI-II, a difference of around 0.5 points (0.18*[3.75-1]=0.50 (to 2 d.p.)] on the PSR for LIFE depression in order to indicate that CBT_{BAR} is having an important effect.

To detect a between-group mean difference of 0.5 points (SD=1.3 points [80]) on the mean 4-week PSR for LIFE depression score at 27-weeks follow-up we require 286 participants with outcome data to achieve 90% power, using an ANCOVA (with 2.5% two-sided significance level), assuming a conservative correlation of 0.4 between baseline and 27-week scores [82]. Inflating the sample size to allow for a conservative 15% attrition (attrition was 13% in our feasibility trial, 57) requires a target to randomise of 338 participants (approx. 68 per site). This sample size will provide greater than 90% power to detect a rather more conservative MID on LIFE PSR for mania (e.g. equating to 98.5% to detect a target effect of 0.25 points [estimated within-group SD=0.5 points]) [80]. In each case, power will be increased due to the (multiple) correlation between outcome and the full set of explanatory variables adjusted for in the model. We have not allowed for a random therapist effect in our sample size calculation as the effect on depression outcome (BDI-II) in our pilot trial was 0, although the confidence interval was wide; we will, however, include the addition of a random therapist effect amongst our sensitivity analyses.

Assuming a standardised effect size of the intervention on the HAPPI of 0.4, 286 participants with mediator and primary outcome data will also allow for 88.5% power for estimation of an indirect effect of 40% via the putative primary mediator (HAPPI), or 83.5% power for the estimation of a 30% indirect effect, based on a total effect on the intervention of the MCID (i.e. 0.5) (with a 2.5% significance level, estimated using the R package medssp, based functions provided in Vittinghoff and Neilands [83]

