4. PARTICIPANT ELIGIBLITY CRITERIA

MAIN TRIAL

Inclusion criteria

The study population are young people meeting BAR criteria. The inclusion criteria are:

- 16-25 years old
- Meet criteria for one of the following:
 - Group I: Sub-threshold mania:
 - For at least 2 consecutive days but less than 7 days: period of abnormally and persistently elevated, expansive or irritable mood + at least 2 criteria from the list (≥ 3 for irritable mood):
 - (1) inflated self-esteem/grandiosity, (2) decreased need for sleep, (3) more talkative than usual, (4) flight of ideas/racing thoughts, (5) distractibility, (6) increase goal directed activity or psychomotor agitation, (7) excessive involvement in activities that have a high potential for painful consequences.
 - **Group II**: Depression + Cyclothymic features:
 - i. Depression (for at least 1 week): depressed mood / loss of interest or please + 2 criteria from the list:
 - (1) significant weight loss, (2) insomnia or hypermania nearly every day, (3) psychomotor retardation/agitation, (4) fatigue/loss of energy, (5) feelings of worthlessness/excessive or inappropriate guilt, (6) diminished ability to think or concentrate, (7) recurrent thoughts of death/suicidal ideation

PLUS

- ii. Cyclothymic features: numerous episodes with sub-threshold manic symptoms not meeting Group 1 criteria: subthreshold mania as defined in Group 1 for 4 hours within 24-hour period and at least 4 cumulative lifetime days in the past 12 months.
- **Group III**: Depression + genetic risk:
 - i. Depression (See Group 2)
 - PLUS
 - ii. Genetic risk: first degree relative with BD
- Help seeking
- Provision of written informed consent

Exclusion Criteria

- History of a treated/untreated manic episode or psychosis of 1-week duration or longer
- Treatment with a mood stabiliser for longer than 6-weeks or antipsychotic for 3-weeks [evidencing exclusion on point above or at the time of the assessment whereby at-risk status cannot be confirmed]
- Organic brain disorder
- Unable to complete assessments due to language barriers
- Inpatient/acute psychiatric care needed
- Primary substance abuse / dependency

NESTED QUALITATIVE STUDIES

All participants will be eligible to take part in the nested qualitative study. This also applies to their family / carers who they might refer to be invited to take part in the nested qualitative study. In addition, stakeholders

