Secondary outcome measures (including the primary outcome measures at time-points other than 27-week) will be analysed using generalised linear models, with link function appropriate to the type of data, adjusted for stratification factors and the baseline value of the outcome measure (where applicable).Time to events (transition to first episode (hypo)mania and recovery from BAR symptoms) will be analysed using a Cox proportional hazards model, adjusted for stratification factors. Tests will use a 5% significance level and two-sided 95% CIs will be presented.

Sensitivity analysis

The alternative method to that used in the primary analysis will be used as a sensitivity analysis (MICE if CCA, or vice versa). Sensitivity analyses will also include the addition of a random therapist effect in a partially-nested model (clustering by therapist in the CBT_{BAR} + TAU arm but no clustering in the TAU arm). A further sensitivity analysis will use longitudinal mixed-effects model incorporating all follow-up time-points (as factors), fitted using maximum likelihood, accommodating the within-participant correlation over time with an unstructured covariance matrix and including stratification factors and the baseline PSRs for depression and mania as covariates.

QUALITATIVE ANALYSIS

Data will be analysed using thematic analysis [96], which provides an accessible and flexible approach, resulting in a rich account of qualitative data. The data generation and analysis will be conducted with leadership and ongoing involvement from individuals with personal experience of the provision of the receipt of this treatment and/or the experience of BAR mood experiences. This involvement is expected to enhance the study during the conduct and analysis of all interviews. We will take a critical realist position, and data will be coded at a manifest level (i.e., analysing only the immediate meaning of participants' language) to produce an accessible body of coded data from which meaningful thematic representations of participants' perspectives can be reported. All semi-structured interviews will be transcribed verbatim and coded systematically and iteratively within NVivo qualitative data analysis software (Version 11, 2016).

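### The transition endpoint is a first (hypo)manic episode, yet people with earlier hypomania can be randomised; separately, the Cox models omit baseline PSRs that would cost little to add

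*Protocol*

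**What the plan says.** **Endpoint.** Protocol section 2 (Secondary Outcome Measurement/Endpoint) uses the SCID-5 at 17, 27 and 52 weeks for "capturing time to transition to first episode (hypo)mania". Efficacy hypothesis 2 in the same section is that CBT_BAR plus TAU "will reduce the likelihood of transition to BD in comparison to TAU alone over a 52-week follow-up time period".

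**Eligibility.** The only exclusion in section 4 based on past episodes is "History of a treated/untreated manic episode or psychosis of 1-week duration or longer". Group I requires elevated, expansive or irritable mood "For at least 2 consecutive days but less than 7 days", with a minimum symptom count and no maximum. No listed criterion, in any BAR group, mentions past hypomania.

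**Related text.** The sample-size text in section 3 says that "those scoring 5-6 will confer research diagnostic criteria and therefore not meet the inclusion criteria for the trial". The Trial Summary abbreviates the criteria and lists entry through mild depressive symptoms with a SCID-5 diagnosis of cyclothymic disorder or bipolar disorder NOS. It also words the endpoint as transition to (hypo)mania, without the word first.

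**Analysis.** Section 8 (Secondary outcomes) states: "Time to events (transition to first episode (hypo)mania and recovery from BAR symptoms) will be analysed using a Cox proportional hazards model", adjusted for stratification factors, which are site and BAR group. The co-primary ANCOVA in section 8 also adjusts for baseline depression and mania PSRs and prior CBT. Other secondary outcomes are adjusted for their own baseline value where one applies.

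**The concern.** The event covers mania and hypomania, but the history exclusion covers mania (and psychosis) only. A person with an earlier hypomanic episode passes the listed criteria. If that person has another episode after randomisation, it cannot be a first one, and calling it a transition to bipolar disorder is doubtful. A hazard ratio that mixes first onsets with recurrences does not cleanly test hypothesis 2, whatever the treatment effect in each group.

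A second, smaller matter sits in the same sentence of section 8. The Cox adjustment is fixed at the stratification factors. The baseline PSRs are collected on everyone and used in the primary model, but are left out here. They are also left out of PSR-derived interval outcomes that have no baseline value of their own, such as the number of well weeks.

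**Working it through.** **1. The passages side by side.**

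| Element | Mania of a week or more | Hypomania |
|---|---|---|
| Endpoint (sections 2 and 8) | counts as an event | counts as an event |
| History exclusion (section 4) | excluded | not mentioned |
| Group I (section 4) | episode must be under 7 days | no symptom ceiling below the 7-day limit |
| PSR 5–6 statement (section 3) | current state only | current state only |

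The mismatch needs no outside diagnostic threshold: one text names mania, the other names (hypo)mania. How large the overlap is does depend on the threshold, which the protocol does not state.

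**2. Is there a planned figure to reproduce?** Not for transition: no event rate, event count or power is given. The primary sample size (286 with data, 338 randomised) does not depend on this point. The only anchor is the pilot odds ratio of 0.40 at 52 weeks (95% CI 0.11 to 1.49; section 6). At an assumed 20% transition under TAU, the treated odds are 0.40 × 0.20/0.80 = 0.10, so the risk is 0.10/1.10 = 0.091 and the hazard ratio is ln(0.909)/ln(0.80) = 0.427. I use 0.425.

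**3. Effect of earlier hypomania on the hazard ratio.** Assumptions: N = 286 (143 per arm), 20% transition under TAU in people without earlier hypomania, share f with earlier hypomania, and a hazard in them either equal to or double that of the rest.

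- Control risk: (1−f)(1−e^−h) + f(1−e^−mh), with h = −ln(0.80) and m = 1 or 2.
- Treated risk: the same, with h multiplied by 0.425 in the first term and by the subgroup's hazard ratio in the second.
- Combined ratio: ln(1−treated risk)/ln(1−control risk).
- Power: Φ(½·√events·|ln HR| − 1.96), two-sided 5%.

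Example, f = 0.10, m = 1, no effect in the subgroup: treated risk = 0.9 × 0.0905 + 0.1 × 0.20 = 0.1015. The ratio is ln(0.8985)/ln(0.80) = 0.479. Events = 143 × (0.20 + 0.1015) = 43.1, and power is 0.675.

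| f | Same effect: HR, power (all) | No effect in subgroup: HR, power (all) | Power, first-onset only (HR 0.425) |
|---|---|---|---|
| 0 | 0.425, 0.79 | – | 0.79 |
| 10% | 0.425–0.427, 0.79–0.81 | 0.48–0.51, 0.68–0.63 | 0.74 |
| 20% | 0.425–0.428, 0.79–0.84 | 0.53–0.59, 0.55–0.49 | 0.69 |
| 30% | 0.425–0.429, 0.79–0.86 | 0.59–0.66, 0.43–0.36 | 0.64 |

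Ranges run from m = 1 to m = 2. Expected first-onset events fall from 41.5 to 41.5 × 0.9, 0.8 and 0.7, that is 37.4, 33.2 and 29.1.

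**4. Effect of leaving out a prognostic baseline.** This used 600 simulated trials per setting, with N = 286, a true hazard ratio of 0.425, a standard normal covariate and a mean control hazard of 0.2 per year (about 36–37 events, so power is lower than in step 3). Site and BAR group were not modelled.

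| Assumed log-HR per SD | Unadjusted HR, power | Adjusted HR, power |
|---|---|---|
| 0.3 | 0.421, 0.70 | 0.420, 0.70 |
| 0.5 | 0.428, 0.66 | 0.418, 0.69 |
| 0.8 | 0.444, 0.59 | 0.421, 0.68 |

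The Monte Carlo standard error of one power figure is about √(0.69 × 0.31/600) = 0.02. The protocol gives no figure for how well PSRs predict transition or recovery.

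**The case against.** **No risk set is written.** A reader might infer that the Cox model keeps people with earlier hypomania at risk, because section 8 analyses as randomised. But that phrase is explained there as analysis by allocated group regardless of treatment received. It does not say who is at risk of a first event, and section 8 leaves complete details to the SAP. This stands, so the model's population cannot be called an error. What remains is a conflict between two protocol definitions, eligibility and endpoint.

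**First may mean first since randomisation.** The Trial Summary's wording allows this, and the endpoint would then be defined for everyone. It would then measure any new episode, which is not the transition to bipolar disorder named in hypothesis 2.

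**Group I is labelled sub-threshold, and PSR 5–6 is said to be ineligible.** The label does not add a history exclusion. The PSR statement concerns state at entry and appears only in the sample-size text. Adjusting for BAR group does not separate these people either: Group I is one stratum and takes priority over the others (section 5).

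**The covariate choice contradicts nothing.** This stands. Randomisation keeps the test valid, and one outcome's model need not copy another's. The Trial Summary also lists the time-in-symptoms outcomes under SCID LIFE with a baseline assessment, so the where-applicable rule may already cover them. The addition is a recommendation only.

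**Conclusion.** The endpoint and the eligibility criteria do not match: a person with earlier hypomania can be randomised, and the first-episode endpoint does not describe a later episode in that person. The share affected is unknown from the protocol.

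A reader might infer that the test of hypothesis 2 is diluted. The documents do not support that as a general claim. Attenuation requires a weaker effect in people with earlier hypomania, and the protocol gives no figure on this. Under the extreme assumption of no effect in 10–30% of the sample, 0.425 becomes about 0.48–0.66. With an equal effect there is essentially no attenuation, and restricting the analysis loses power. The firm conclusion is about what the hazard ratio means, not about its size.

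Omitting the baseline PSRs is not an error. Including them brings a gain from negligible (0.70 against 0.70) to modest (0.59 to 0.68), depending on an assumed prognostic strength.

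**What to change.** 1. Reconcile the Trial Summary criteria, the PSR 5–6 statement in section 3 and the criteria in section 4 with the endpoint, and state the SCID-5 definition of the event.
2. From the baseline SCID-5 mood modules, prespecify the first-onset analysis in participants with no earlier episode meeting that event definition. Status is fixed before randomisation, so the comparison remains a randomised one. The sponsor should confirm that past hypomania is recorded at baseline, not only current state.
3. Keep an all-randomised analysis alongside, labelled as any (hypo)manic episode after randomisation.
4. Add baseline mania and depression PSRs to both Cox models (transition and recovery), and to PSR-derived interval outcomes that have no baseline value of their own, such as well weeks.

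**Cost.** The changes are to wording, provided past hypomania is recorded; PSRs are already collected at baseline. The first-onset analysis has fewer events, about 29–37 instead of 41.5 under the assumptions above. Two PSR terms also lengthen a model with treatment (1), site (4) and BAR group (2): 9 parameters, or 41.5/9 = 4.6 events each. The sponsor should weigh that if transitions are few.
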